unintended sign (including an abnormal laboratory finding), symptom or disease temporally associated with the use of the study device, whether or not related to the study device.

Reporting of Adverse Events

Only AEs that occur during or following study treatment with the drug will be reported in the AE section of the source documents. Events recorded prior to study treatment with the drug will be reported in the Medical History section of the source documents as appropriate. All AEs occurring during the course of the study will be individually recorded in the source documents. A condition that is present prior to administration of study drug and that worsens after administration of study drug should be reported as an AE. Information regarding the onset, duration, severity, action taken, outcome, and relationship to study drug will be recorded. New or worsening abnormal laboratory values and/or vital signs are to be recorded as AEs if they are considered to be of clinical significance by the PI or meet the criteria of an SAE (see below). Unless a diagnosis is available, signs and symptoms must be reported as individual AEs in the source documents; a diagnosis is preferred.

Adverse events (AEs) will be monitored throughout the study. Subjects will be instructed to inform the Principal Investigator (PI) and/or study staff of any AEs. At each visit, subjects will be asked about AEs in a non-specific manner using open-ended questions so as not to bias the response (e.g., Has the subject had any changes since the last visit?). Specific inquiry regarding reported AEs will be conducted when applicable. All adverse events will be documented and recorded in the source documents.

Any subject who has an AE (whether serious or non-serious) or clinically significant abnormal laboratory test value will be evaluated by the PI and will be treated and/or followed up until the symptoms or values return to normal or to clinically acceptable levels, as judged by the PI. A physician, either at clinical site, or at a nearby hospital emergency room, will administer treatment for any serious adverse events (SAEs), if necessary. When appropriate, medical tests and examinations will be performed to document resolution of event(s).

Intensity Grading of AEs

The severity of an AE will be designated as mild, moderate or severe. The term "severe" is used to describe the intensity of an adverse event; the event itself, however, may be of relatively minor clinical significance (e.g. 'severe' upper respiratory infection). Severity is not the same as "serious". Seriousness of AEs is based on the outcome/action of an AE.

Causality and Relatedness

The relationship of the AE to the study treatment will be based on the following two definitions:

Not related: An AE is defined as "not related" if the AE is not judged to be associated with the study treatment and is attributable to another cause;

Related: An AE is defined as "related" where a causal relationship between the event and the study treatment is a reasonable possibility (possibly or probably related). A reasonable causal relationship is meant to convey that there are facts (e.g., evidence such as dechallenge/ rechallenge) or other clinical arguments to suggest a causal relationship between the AE and study treatment.

Serious Adverse Events

Definition of Serious Adverse Events

An SAE is defined as any untoward medical occurrence that, at any device setting or dose:

- Results in death;
- Is immediately life-threatening (i.e., in the opinion of the PI, the AE places the subject at immediate risk of death; it does not include a reaction that, had it occurred in a more severe form, might have caused death);
- Requires inpatient hospitalization or results in prolongation of an existing hospitalization;
- Results in persistent or significant disability or incapacity;
- Is a congenital anomaly or birth defect;
- Is an important medical event that may not be immediately life-threatening, results in death, or require hospitalization, but may be considered an SAE when, based upon appropriate medical judgment, it jeopardizes the subject or may require medical or surgical intervention to prevent one of the outcomes listed above.

Reporting Serious Adverse Events

As soon as the PI becomes aware of an AE that meets the criteria for an SAE, the SAE should be documented to the extent that information is available. A report must be submitted by the study site to the SLU IRB, within 24 hours. Forms for reporting SAEs will be provided to the study site. SAEs will be recorded from the time of informed consent, through the end of the study. If in the opinion of the Investigator, an SAE occurring outside the specified time window (i.e., following subject completion or withdrawal from the study), is deemed to be device related, then the event should be reported with 24 hours as outlined above. The Investigator should institute any clinically necessary supplementary investigation of SAE information.

Death

In the case of subject death, any post-mortem findings/reports will be requested and a report (even if a preliminary diagnosis/cause of death is available) will be submitted to the SLU IRB within 24 hours of learning about the death.

Reporting of Pregnancy

In the case of subject pregnancy, the subjects will be discontinued from the study and will be followed leading up to delivery.

Data Analysis and Statistical Considerations

At the completion of the study, the data obtained will be reviewed and analyzed with the aid of the Saint Louis University Center for Health Outcomes Research. A chi-square test along with the Wilcoxon signed rank test will be performed to assess significant difference between clinical improvement scores between study visits. There is no data to suggest that there is a difference in the appearance of older (more than 1 year old from the initial injury) and newer scars post-therapy. We will aim to recruit 20 patients with old scars (10 of which will be in the high energy treatment group, and 10 of which will be in the low energy treatment group). In terms of statistical analysis, we will review whether there is a difference between the post-treatment measurements and appearance of older scars and newer scars.

Quality Control and Quality Assurance

Quality control and assurance for this study will be performed by an internal review every 3 months to ensure that the data collected is in accordance with the goals of this study and to address any issues with data collection or performance of any study procedures.

Direct Access, Data Handling and Record Keeping

Access to all study materials will be kept in a locked facility within the SLU Dermatology Des Peres Office. Only staff members will have access to this room. With respect to the randomization spreadsheet, only the principle investigator will have access to this information. This information will be kept in a locked file cabinet in her office. The source documents created by the study site will be the primary forum for recording study data. When the study is completed, these documents will be placed in a long term storage facility owned by SLU.

Confidentiality

Interested subjects will sign a HIPPA form allowing access to relevant medical records. All study data will remain confidential, unless it is deemed by the principle investigator and/or research team members that it is important for the patient's health for study participation to be disclosed to appropriate parties (i.e. other medical providers). Study materials for each subject will have a deidentified code, such as subject Jane Doe is subject 001.

Data Protection

The master list, which will be password-protected, will be kept confidential to all research staff except the principle investigator. She will be the only unblinded individual in this study who will set the password for this document and will have access to the master list. Study materials for each subject will have a deidentified code, such as subject Jane Doe is subject 001.

Records Retention

Records will be retained within a locked office within the SLU Dermatology Des Peres Office

Posting to Clinical Trials Register and Publication

Information about this study will be posted to the Clinical Trials Register (accessible via http://www.clinicaltrials.gov). Recruitment for the study will be open until the study has obtained 50 patients. All recruitment information posted to the Clinical Trials Register will be reviewed and approved by the SLU IRB. Final data analysis and publication will be between July and August 2017.

References

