This study evaluates the effect of a fractionated carbon dioxide laser on surgical scars of the face and neck over 12 months. Anyone with a surgical scar on the face and neck who has not had laser therapy may be eligible. The visits occur every three months for up to 12 months. Subjects will be randomly assigned to receive two high energy treatments or two low energy treatments. During the study visits, the scars will be photographed pre-treatment and the subject will complete a questionnaire to rate the scar. Three physicians will also evaluate the scar: one as a live assessment and the other two will evaluate the scars after each visit using photographs. Patients will receive their assigned treatment, obtain post-treatment instructions, and a diary to record redness, swelling, pain, itching, or other skin changes after treatment. Patients and raters will be blinded to which therapy level the patient receives until the 9-month visit (Visit #3) at which time patients will be unblinded and offered to have a third high energy treatment if in the high energy treatment group or to have two high energy treatments if in the low energy treatment group.

Study Timeline

The study will occur over 14 months. Our tentative timeline consists of recruitment and screening to occur in November 2016-September 2017. Study visits and data collection would occur between November 2016 and September 2017. Preliminary data analysis and publication of preliminary results would occur between August 2017 and March 2018. Final data analysis and publication would be between October 2018 and January 2019.

Introduction

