the subject tends to form keloid scars or scars from minor trauma. Also, the subject should not participate in the study if the subject has taken oral isotretinoin medication within the past 6 months. In addition, the principle investigator may exclude the subject from the study if she determines that the study may put the subject at risk. The subject will provide written consent (permission) to be a participant in the study and for the research team to access the subject's health information to learn more about the surgery that resulted in the scar and the original features of the scar. Immediately before any study visit, the subject will be asked to not wear any make-up or use facial moisturizers (or moisturizers on the neck). The subject will be asked to cleanse their face with a gentle cleanser, such as Cetaphil, provided in the office prior to treatment.

Other procedures at this visit:

- The subject will have photographs taken of the scar that will be shared confidentially with two other research physicians in the study for them to answer questions about the scar.
- The subject will complete a questionnaire about the scar and another research physician will see the subject at this visit to evaluate the scar.

If the subject qualify for study treatment the following may occur at the same visit or at a return visit within 30 days. The following will occur:

- If the subject has a history of recurrent fever blisters/cold sores on the lips or face, The subject will be offered a three day prescription for an antiviral medication that the subject can fill at the subject's pharmacy to prevent a recurrence since laser treatments may increase the chance of recurrent episodes. The subject would take one pill every twelve hours the day prior to treatment, on the treatment day, and the first day post-treatment. The subject or their insurance plan must cover the cost of the medication. This may delay the treatment to a later date within 30 days of the screening visit.
- The subject will complete a pre-treatment questionnaire.
- The subject will receive laser treatment as randomized to either high energy or low energy treatment which includes:
 - Prior to treatment, the subject will be asked to cleanse his or her face with a gentle cleanser, such as Cetaphil, provided in the office in order to remove all lotion, creams, make up, and sunscreen.

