This visit occurs 3 months after the subject's second treatment with the following activities:

- The subject will return the diary
- The subject will complete a questionnaire
- o The subject will undergo scar evaluation by the research physician
- The subject will have photographs taken
- The treating investigator will let the subject know which treatment the subject received
- o If the subject received the high energy laser treatment, the following will occur:
 - The subject will be offered the option to receive a third high energy treatment.
 - If the subject accepts treatment today, the subject will return in 3 months for the final follow up visit and to exit the study
- o If the subject declines further treatment, the subject will be exited from the study at this visit.

If the subject received the low energy laser treatment, the following will occur:

- The subject will be offered the option to receive two high energy treatments.
 - o If the subject accepted treatment, the subject will receive one treatment today and return in 3 months for the second treatment (Visit 4); the subject will then be asked to return 3 months later for a follow up final study visit (Visit 5).
- o If the subject declined further treatment, the subject will be exited from the study.

Study Visit #4

If the subject were originally treated with the high energy laser, and elected a third treatment at Visit 3, this visit occurs 3 months after the subject's Visit 3 treatment with the following activities:

- The subject will return the subject's diary
- o The subject will complete a questionnaire
- The subject will undergo scar evaluation by the research physician
- The subject will have photographs taken
- The subject will be exited from the study

If the subject were originally treated with the low energy laser, and elected treatment with the high energy laser, this visit occurs 3 months after the subject's Visit 3 treatment with the following activities:

- o The subject will complete a pre-treatment questionnaire
- The subject will receive the last high energy laser treatment The subject will obtain post-treatment instructions
- The subject will obtain a paper diary to record possible reactions such as redness, swelling, pain, itching or color changes following treatment

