Patients who require evaluation outside of the three month windows +/- two weeks due to a related adverse event will be evaluated by the research team at the earliest convenience. If the nature of the evaluation is in regards to an adverse event/significant adverse event, a severe cutaneous reaction to the laser, or having an unrelated cosmetic procedure involving the study scar during the study, staff will evaluate the patient accordingly, document the event, and report any serious adverse events to the SLU IRB within a 24 hour window.

Completion of Study

At the completion of the study, the data obtained will be reviewed and analyzed with the aid of the Saint Louis University Center for Health Outcomes Research. This data will then be presented in the form of a paper and/or scientific poster. At the completion of the study, the data obtained will be presented in the form of a scientific paper and/or scientific poster.

Methods of Assigning Subjects to Treatment Arms

In terms of randomization, a spreadsheet will be created by the principle investigator with the aid of the research staff to predesignate the treatment assignment. For each patient that comes in, the principle investigator will use that as a guide to dictate the treatment arm assigned for that subject.

Blinding

Other than the investigating physician performing the laser treatment, no one (including the subjects, study coordinators, and the physicians who will be evaluating the response to treatment) will know who is receiving the high energy treatment or the low energy treatment until Visit #3.

Unblinding

At the Visit #3, subjects and the investigating physician performing the treatments will know the type of treatment that the subject in question received.

Concomitant Treatments

Prohibited

Patients will be prohibited from obtaining any additional cosmetic procedures during the study (i.e. dermabrasion, chemical peels) that may interfere with the interpretation of the results of the study.

Permitted

Patients will be permitted to continue using the moisturizers and cleansers that they have been using for the last 6 months. Patients will be allowed to take all oral medication (except isotretinoin) throughout the study.

Benefits and Alternatives

Benefits

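### The stated rater blind ends at Visit 3, but two of the three physicians score the Visit 3 photographs after that visit, so the plan does not guarantee blinding for those scores

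*Combined protocol and SAP*

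**What the plan says.** The opening summary sets the end of the blind: "Patients and raters will be blinded to which therapy level the patient receives until the 9-month visit (Visit #3"). The same paragraph gives the three physicians' roles: "one as a live assessment and the other two will evaluate the scars after each visit using photographs".

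The Blinding section repeats the limit, with an exception for whoever operates the laser. On everyone else it says: "no one (including the subjects, study coordinators, and the physicians who will be evaluating the response to treatment) will know who is receiving". This holds only up to Visit #3 ("will know who is receiving the high energy treatment or the low energy treatment until Visit #3"). The evaluating physicians are named in that sentence.

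Three other places bear on the point:

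- **Unblinding section:** "At the Visit #3, subjects and the investigating physician performing the treatments will know the type of treatment that the subject in question received". Raters are not mentioned.
- **Data Protection**, on the principal investigator: "She will be the only unblinded individual in this study". No time limit is given.
- **Study Visit #3:** the questionnaire, the live scar evaluation and the photographs are listed first, followed by "The treating investigator will let the subject know which treatment the subject received".

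On how the photo raters receive images, Study Visit #1 mentions only "photographs taken of the scar that will be shared confidentially with two other research physicians in the study". No section describes removal of visit labels, coding of images for reading, or reading order.

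**The concern.** Two separate kinds of knowledge could reach the photo raters.

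**Knowledge of the arm.** The observer POSAS is a subjective score. A rater who knows the arm may score high-energy scars more favourably, and that error goes straight into the comparison between arms. Study Procedures relies on the assessment three months after the second treatment to compare all subjects after two treatments. After Visit 3, high-energy subjects may take a third treatment and low-energy subjects may switch to high energy, so no later visit can replace that randomised comparison. Masking lost at this visit cannot be restored in the analysis.

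**Knowledge of the visit.** A rater who knows that one image is pre-treatment and another post-treatment may expect improvement. The Data Analysis section names a chi-square test and a Wilcoxon signed rank test for differences between study visits, so expectation of this kind acts directly on the quantity tested.

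**Working it through.** The plan gives no figure on this point, so there is none to reproduce. The check compares when the blind ends with when ratings are made.

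**1. Ratings at Visit 3**

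| Rating | When it is made | Covered by a blind lasting until Visit 3? |
|---|---|---|
| Patient questionnaire | At the visit, listed before disclosure | Protected if the listed order is followed |
| Live physician | At the visit, listed before disclosure | Protected if the listed order is followed |
| Photo physician 1 | After the visit | No |
| Photo physician 2 | After the visit | No |

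With 50 subjects (Study Population) and three physician raters, there are 3 × 50 = 150 physician ratings at Visit 3, of which 2 × 50 = 100 are photo ratings. This assumes that every subject attends and has one scored scar segment.

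**2. Who may learn the arm at Visit 3**

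- The summary and the Blinding section end the raters' blind at Visit 3.
- The Unblinding section lists only subjects and the treating physician.
- Data Protection treats the principal investigator as the sole unblinded person, and restricts the randomisation list to that role. This cannot hold literally once subjects are told, and it does not fit a rater blind that stops at Visit 3.

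Staff could follow the first pair exactly and tell a photo rater the arm before scoring. Staff who follow the other two would not. No section settles which governs.

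**3. What visit-by-visit scoring reveals**

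Up to Visit 3 both arms have the same visits, so reading order does not reveal the arm. It does reveal the visit: the first images a rater receives for a subject are the baseline ones. The subject codes in the Confidentiality section hide identity, not visit.

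**4. Which comparison each kind of knowledge affects**

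Let T be the true change in an arm, b the error from knowing the visit, and a the extra error from knowing that the arm is high energy.

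- Visit known, arm unknown: observed change is T + b in each arm. The difference between arms is (T_high + b) − (T_low + b) = T_high − T_low, so b cancels if it is the same in both arms. A between-visit test still tests T + b.
- Arm also known: the difference between arms is T_high − T_low + a, and a does not cancel.

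The visit problem therefore bears on the between-visit tests that the plan names. The arm problem bears on the comparison of the randomised groups.

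**5. Later visits**

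At Visit 4 a high-energy subject is assessed and exits, while a crossed-over low-energy subject is treated. Only crossed-over low-energy subjects reach Visit 5. If Visit 3 images are scored late and still carry visit information, this pattern could reveal the arm.

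**6. Visit label**

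Visit 3 falls 3 + 3 = 6 months after the first treatment. Allowing the 30-day delay to first treatment and a two-week window on each interval, the latest is about 1 + 3.5 + 3.5 = 8 months from screening. The summary's label of 9 months does not fit. This is a separate inconsistency and does not change the point, because both statements of the limit also name Visit #3.

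**The case against.** The strongest reply is that this is loose drafting, not a plan to unblind raters. In the summary, the sentence that ends the blind goes on to name only patients as being unblinded. The Unblinding section does not list raters, and the list stays with the principal investigator. The Visit 3 steps already place the patient rating, live rating and photographs before disclosure. The imaging and measurement instructions are deferred to a separate document, which might cover image handling.

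Most of this stands. A reader might infer that the plan has raters unblinded at Visit 3; the documents do not say so. A reader might infer that all Visit 3 ratings are exposed; the listed order protects the patient and live ratings, although the plan does not expressly require that order. A reader might also infer that scoring in time order gives away the arm; up to Visit 3 it cannot, and reading order is itself an inference from scoring after each visit.

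The gap remains all the same. Two sections end the raters' blind at Visit 3, and none extends it until the photographs from that visit are scored. The separate document is described as covering how images are taken and scars measured, not how raters are masked.

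**Conclusion.** The point holds in a limited form. The stated blind does not cover the Visit 3 scores of two of the three physician raters, and those scores contribute to the last randomised comparison before crossover. Disclosure of the arm to these raters is permitted by the wording but not planned, so this is a gap in the guarantee and not evidence that unblinding will occur. The visit-knowledge problem rests on reading the scoring as taking place visit by visit, which is the natural meaning of the text.

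The size can be given only as exposure: up to 100 of 150 physician ratings at Visit 3, on the assumptions shown. A reader might want an inflated false-positive rate. The documents do not support one: they give no size for a rating shift, do not plan the disclosure, do not say how the three physicians' ratings are combined, and name no between-arm t-test from which to compute it.

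**What to change.** Amend the summary and the Blinding section to say that:

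- at Visit 3 only the subject is told the arm, after the patient rating, live rating and photographs have been recorded, which makes the order already listed under Study Visit #3 a requirement;
- the live rater stays blinded through the Visit 3 rating;
- the two photo raters stay blinded until all photo scores are locked.

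Replace photo scoring after each visit with batch scoring of coded images, in random order, with visit and arm labels removed. Reconcile the Unblinding and Data Protection sections with this wording, including the statement that only one person is unblinded.

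Do not promise a blinded live rater at Visits 4 and 5. Attendance and the activities at those visits reveal the arm, so live ratings made there should be reported as potentially unblinded.

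The cost is a wording amendment, coding of images by existing staff, and photo scores that become available later. The preliminary analysis, scheduled to begin in August 2017, may have to wait for them or proceed without them. No visit, procedure or subject burden is added. The change should be in place before any Visit 3 images are scored.
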